5.3 Additional Study Restrictions

5.3.1 Contraception

The investigator should review the sexual maturity of study patients on a regular basis and provide guidance on the use of contraception, as necessary, while the patient is participating in the study.

Participating patients that are sexually mature and sexually active must be willing to use contraception (ie, condom) for the duration of the study.

5.3.2 Social Media

Patients and caregivers must not post any study-related information on social media. Posting study related information on social media sites may have a negative impact on the study and potentially result in patient discontinuation from the study.

5.4 Withdrawal and Study Treatment Discontinuation

Patients are free to withdraw from the study or discontinue study treatment at any time, upon request, without prejudice to their future medical care by the Investigator or at the study site. See Section 4.1.4 for study specific requirements. Patient participation in the study may also be stopped at any time at the discretion of the Investigator or at the request of the Sponsor, as described below.

5.4.1 Withdrawal of Patients from the Study

Patients must be withdrawn from the study for any of the following:

- The patient or patient's legal guardian(s) withdraws consent.
- At the discretion of the Investigator for medical reasons
- At the discretion of the Investigator or Sponsor for noncompliance
- Significant protocol deviation
- Termination of the study by the Sponsor (See Section 15.4 for additional details).

Any patient for whom consent to participate in the study is withdrawn will be removed from further treatment and study observation immediately upon the date of request. These patients should complete the early termination study procedures ([Table 1](#)) and observations at the time of withdrawal. The reason for withdrawal from the study must be recorded in the eCRF and source documentation.

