4.1.4 Discontinuation and Withdrawal

Patients who discontinue study treatment prior to study completion, will be encouraged to remain in the study to be monitored and to complete all study related procedures until study completion.

Patients withdrawing from the study will be requested to come back to the clinic for an early termination (ET) visit ([Table 1](#) [ET visit for double-blind period] and [Table 2](#) [ET visit for OL period]) to have relevant safety and efficacy assessments performed.

Any patient, for whom consent to participate in the study is withdrawn, will be removed from further treatment and study observation immediately upon the date of request.

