11.2.1 Analysis Populations

The primary efficacy analysis population will be the intent-to-treat (ITT) population, which consists of all randomized patients. All patients will be analyzed according to the treatment to which they are randomized.

The safety population will include all randomized patients who have received at least one dose of the study drug. All patients will be analyzed according to the treatment they have actually received.

The pharmacokinetic population will be a subset of the safety population and include subjects with evaluable pharmacokinetics data.

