11.3.2 Analyses of Efficacy Endpoints

11.3.2.1 Analysis of dystrophin protein level

A primary objective of this Phase 2/3 study is to evaluate the efficacy of WVE-210201 by assessing changes in dystrophin protein levels. Therefore, the primary efficacy endpoint for the United States and Other regions, as applicable, and the key secondary endpoint for the EU and Japan is the change in dystrophin protein level (% normal) from baseline. The treatment policy estimand, which assesses the effect of treatment initially assigned at baseline (regardless of adherence to the planned course of treatment), will be used. The analysis population will be the ITT population. The main estimator is a Bayesian analysis of covariance (ANCOVA). The model will include fixed effects for mean change from baseline in dystrophin levels at each time point for placebo and fixed effects for the increase or decrease in dystrophin compared to placebo for each treatment arm at each time point.

Let the change from baseline in dystrophin level at time point j for patient i be Y_{ij} , for $j = 1, 2, 3$ and $i = 1, \dots, n$. Time periods $j = 1, 2$, and 3 , refer to the post-baseline visits at 12, 22 and 46 weeks; each patient will have one Y_{ij} with either $j = 1, 2$, or 3 . The ANCOVA model is

$$Y_{ij} = \alpha_j + \theta_{t(i),j} + \epsilon_{ij};$$

$$\epsilon_{ij} \sim N(0, \sigma_{t(i),j}^2).$$

The $\alpha_j, j = 1, 2, 3$, parameters represent the mean change from baseline in dystrophin level at each time point for placebo-treated patients. For patient i , the treatment arm is labelled $t(i)$ with 0 for placebo, 1 for WVE-210201 3 mg/kg and 2 for WVE-210201 4.5 mg/kg. The effect of treatment T at time j is the parameter $\theta_{T,j}, T = 0, 1, 2$ and $j = 1, 2, 3$. For placebo, the effect is assumed to be 0 ($\theta_{0,j} = 0$). Thus, the treatment effect parameter for treatment T at time j represents the mean difference in the change from baseline in dystrophin at time j compared to placebo. The errors for the individual observations, ϵ_{ij} , are assumed independent and follow a normal distribution. The standard deviation, $\sigma_{T,j}, T = 0, 1, 2$ and $j = 1, 2, 3$, is specific to treatment arm and visit.

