11.3.2.2 Analysis of North Star Ambulatory Assessment (NSAA)

Another primary objective is to evaluate the efficacy of WVE-210201 by assessing changes in the NSAA. Therefore, the primary efficacy endpoint for the EU and Japan and the key secondary endpoint for the United States and Other regions is the change in NSAA from baseline over 48 weeks. The treatment policy estimand which assesses the effect of treatment initially assigned at baseline (regardless of adherence to the planned course of treatment) will be used. The analysis population will be the ITT population. The main estimator will be a Bayesian progression model (BPM) to compare the change in NSAA between patients treated with WVE-210201 and placebo treated patients^{59,60}. The placebo data from this study will be augmented with historical control data via a Bayesian meta-analytic approach.

The BPM assumes a non-parametric rate of progression of the NSAA for placebo patients and a proportional rate of slowing NSAA progression for the treated patients relative to the placebo patients at each time point. The model will include covariate effects to measure differences in the rates of progression based on patient-specific baseline covariates. Additionally, random patient variability will be accounted for using patient-level random effects of the rate of NSAA progression. Borrowing from historical control data to augment the placebo arm information will entail including a random data source effect to model the between-source variability in NSAA progression rates.

The NSAA analysis will be independent of the dystrophin analysis described in [Section 11.3.2.1](#). Let the NSAA at visit j for patient i be Y_{ij} , for $j = 0, \dots, 4$ and $i = 1, \dots, n$. The Y_{i0} observation corresponds to the baseline visit. Visits $j = 1, 2, 3, 4$ refer to the post-baseline visits (each separated by 12 weeks). Let X_i be a vector of dimension C of baseline covariates for patient i that have been standardized. The DPM is

$$Y_{ij} = \gamma_i + \exp(\theta_{t(i)} + \eta_i + \alpha X_i + \delta_{s(i)}) \sum_{k=0:j} \beta_k + \epsilon_{ij}; \\ \epsilon_{ij} \sim N(0, \sigma_{t(i),s(i)}^2).$$

Patient-specific random effects, $\gamma_i, i = 1, \dots, n$, represent the patient-specific mean NSAA at the time of randomization.

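### Withdrawing boys from the study for a significant protocol deviation or for noncompliance conflicts with the treatment-policy estimand; dystrophin is affected most

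*Combined protocol and SAP*

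**What the plan says.** Section 5.4.1 opens with "Patients must be withdrawn from the study for any of the following". Two entries on the list concern conduct rather than consent or health: "At the discretion of the Investigator or Sponsor for noncompliance" and "Significant protocol deviation". The second carries no discretion, and the protocol does not define it; Section 15.3.2 defines only a major deviation. Section 7.3 adds that a patient may be withdrawn from the study once his blind is broken.

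Section 11.2.1 sets the analysis population: "The primary efficacy analysis population will be the intent-to-treat (ITT) population, which consists of all randomized patients". For dystrophin (primary for the US and other regions), Section 11.3.2.1 adopts a treatment-policy estimand that "assesses the effect of treatment initially assigned at baseline (regardless of adherence to the planned course of treatment". Section 11.3.2.2 gives the same definition for NSAA (primary for the EU and Japan).

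On follow-up, Section 4.1.4 says "Patients who discontinue study treatment prior to study completion, will be encouraged to remain in the study", and Section 5.4.2 repeats this. Both statements concern boys who stop treatment. Boys who leave the study are asked for one early termination visit, which includes NSAA (Table 1), and they are not replaced (Section 5.4.4).

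Each boy has one post-baseline biopsy: Week 12 for the first 30, Week 22 for the next 40, Week 46 for the rest (Section 4.1.2). Dystrophin missing because of study discontinuation is set to baseline (Section 11.3.2.1). For NSAA, treated boys' missing scores, and scores collected after they stop randomized therapy, are imputed from control; placebo boys' missing scores are imputed as missing at random (Section 11.3.2.2).

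**The concern.** A treatment-policy estimand needs the outcomes of boys who missed infusions or departed from the protocol. Section 5.4.1 makes those same events grounds for ending observation. What could have been measured is then imputed, and a post-randomization judgement by the investigator or sponsor helps decide who is measured.

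At stake are the single dystrophin value of any boy withdrawn before his biopsy, and NSAA visits after the early termination visit. Boys assigned to the Week 46 biopsy are exposed to the rule longest, and the final dystrophin test rests on that time point alone.

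**Working it through.** **Does another section resolve the conflict?**

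| Event | Rule | Later data |
|---|---|---|
| Boy stops treatment | Encouraged to stay (4.1.4, 5.4.2) | Collected |
| Significant protocol deviation | Must leave the study (5.4.1) | One early termination visit |
| Noncompliance | Leaves at investigator or sponsor discretion (5.4.1) | One early termination visit |
| Blind broken | May be withdrawn (7.3) | One early termination visit, if withdrawn |

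The stay-in-study wording does not reach the last three rows. Table 1 refers the biopsy to Section 4.1, which names only Weeks 12, 22 and 46, so the early termination visit is not stated to recover it.

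**The plan's own power figure.** Inputs from Section 11.1: difference 3.0, SD 4.5, two-sided 5%, 150 boys, 10% dropout. The 1:1:2:2 ratio gives 50 pooled placebo and 50 per dose, or 45 each after dropout. The noncentrality is 3.0 / (4.5 × √(1/45 + 1/45)) = 3.16 on 88 degrees of freedom, giving power of 87.9%. The stated 88% is reproduced for one dose against pooled placebo. Pooling the doses (45 against 90) gives 95.2%.

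**Dilution.** Let w be the fraction of treated boys removed under these entries. If each would have shown the full effect and is instead given a control-like NSAA course or zero dystrophin change, and placebo dystrophin does not change, the loss is w × 3.0 for NSAA and w × 4.0 for dystrophin. The documents give no w. The values 0.6% and 2.7% are the total discontinuation rates that Section 11.3.2.1 cites from earlier pivotal studies; 5% and 10% are assumptions.

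| w | NSAA loss (points) | Dystrophin loss (points) | NSAA power, one dose | NSAA power, pooled doses |
|---|---|---|---|---|
| 0.6% | 0.006 × 3.0 = 0.02 | 0.006 × 4.0 = 0.02 | not calculated | not calculated |
| 2.7% | 0.027 × 3.0 = 0.08 | 0.027 × 4.0 = 0.11 | 86.1% | 94.1% |
| 5% | 0.05 × 3.0 = 0.15 | 0.05 × 4.0 = 0.20 | 84.4% | 93.1% |
| 10% | 0.10 × 3.0 = 0.30 | 0.10 × 4.0 = 0.40 | 80.4% | 90.4% |

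The power columns use the t-test with effect 3.0 × (1 − w), SD 4.5, and the 10% dropout already taken off. They illustrate size only; the planned analysis is a Bayesian progression model.

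**One boy's weight in the dystrophin tests.** Section 11.5.1 allows up to 80 boys at Week 46, so 80 × 2/6 = 26.7 on 4.5 mg/kg. One such boy set to zero change costs 4.0 / 26.7 = 0.15 points. At the first interim, 30 × 2/6 = 10 per dose, and one boy costs 4.0 / 10 = 0.4 points. The second figure assumes that the 46-week effect applies at Week 12.

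**What is avoidable for NSAA.** Section 11.3.2.2 discards treated boys' scores after therapy stops even when they were collected. Editing Section 5.4.1 alone would therefore recover only the scores of treated boys who would have stayed on drug, and those of placebo boys. The NSAA column above overstates what that edit would save.

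**The case against.** The rule is softer than it first appears. A reader might infer that every noncompliant boy has to be removed. That entry is discretionary, and Section 5.4 itself says only that participation may be stopped. The deviation entry is what carries the conflict, and nothing in the documents softens it.

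A reader might also infer that the data the estimand needs are wiped out. They are not. Scores before withdrawal stay in the analysis, the early termination visit adds an NSAA, and a biopsy already taken at Week 12 or 22 is kept.

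Nor do the documents support a claim of steered or unpredictable bias. Section 7.1 keeps study personnel blinded, and Section 11.5 denies interim results to the sponsor staff who run the trial. For treated boys both imputation rules pull a true effect towards none. For placebo boys the direction depends on whether missing at random holds, on which the documents are silent.

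On size, the cited discontinuation rates of 0.6% and 2.7% cover all causes, so these two entries would account for only part of any such total. A noncompliant boy would probably have shown less than the full effect. The sample size already allows 10% dropout, and the pooled NSAA comparison keeps 93.1% power at w = 5%.

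All of this limits the size. None of it reconciles the text: the deviation entry still ends follow-up while the estimand counts such boys, and a biopsy not yet taken is still replaced by zero change.

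**Conclusion.** The inconsistency is real and modest in size. It is clearest for dystrophin, where withdrawal before the biopsy leads straight to baseline imputation. For NSAA the avoidable loss is limited to on-treatment scores and placebo scores, and the larger departure from the stated estimand lies in Section 11.3.2.2.

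The dilution figures are ceilings. They assume the full effect in every removed boy, complete replacement by control-like or zero-change values, and no placebo dystrophin change. At the discontinuation rates the protocol cites, the ceilings are 0.02 to 0.08 NSAA points and 0.02 to 0.11 dystrophin points. The actual rate under these entries is unknown. The point does not show that either primary analysis would fail. It shows that outcomes would be lost avoidably, and an assessment not made at its scheduled time cannot be recovered later.

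**What to change.** - **Section 5.4.1:** remove noncompliance and significant protocol deviation as reasons for withdrawal from the study. State that these boys stay in scheduled follow-up, including NSAA visits and the second biopsy already planned, unless consent is withdrawn or the existing medical-reasons entry applies.
- **Section 7.3:** reconcile the wording on withdrawal after unblinding in the same way.
- **Section 11.3.2.2:** use NSAA collected after treatment discontinuation as observed, in line with the stated estimand, and keep imputation for scores that are truly missing. Without this, the first change does little for treated boys who stop drug.

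Whether study drug continues stays with the existing rules; nothing here changes them.

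The cost is protocol wording, some additional visits that are already on the schedule, and planned second biopsies in boys who would otherwise have left. The biopsy is an open surgical procedure in a child, which is why the consent and medical-reasons exceptions should be written out.

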5.4.2 Discontinuation of Study Treatment

A patient may permanently discontinue study treatment for any of the following:

- The patient is withdrawn from the study ([Section 5.4.1](#)).
- The patient experiences a serious or intolerable AE that in the Investigator's opinion requires treatment discontinuation (*e.g., severe or serious reactions during infusion, such as hypotension requiring treatment, dyspnoea requiring bronchodilators, angioedema or generalized urticaria require immediate discontinuation of the study drug administration, aggressive symptomatic therapy, and the patient should not be re-challenged.*).
- A change in the patient's medical condition not consistent with the protocol requirements or that justifies withdrawal from the study or study drug.

If a patient discontinues treatment, they will be encouraged to remain in the study to be monitored and to complete all study related procedures, unless consent is withdrawn. Patients who discontinue treatment due to an AE ([Section 9](#)) may require longer follow-up.

The reason for discontinuation of study treatment must be recorded in the eCRF and source documentation.

5.4.3 Lost to Follow-up

Patients who fail to return for study assessments will be contacted by the site in an attempt to have them comply with the protocol. A minimum of three documented contact efforts should be made on different days over the course of 2 weeks. If the patient is unreachable by telephone, a registered letter will be sent to the patient or the caregiver requesting him/her to contact the study center. As part of the informed consent, patients will be asked if they are willing to be contacted at the follow-up time point if they have stopped study participation.

5.4.4 *Replacements*

Patients who withdraw from the study will not be replaced.

6 INVESTIGATIONAL DRUG AND PLACEBO

6.1 Method of Assigning Patients to Investigational Drug or Placebo

Treatment will be assigned through randomization performed using a centralized, interactive voice/web response system (IXRS).

6.1.1 *Double-blind Treatment Period*

Patients will be randomized in a 1:1:2:2 ratio to placebo 3 mg/kg, placebo 4.5 mg/kg, WVE-210201 3 mg/kg, and WVE-210201 4.5 mg/kg. Randomization will be stratified by age (≤ 9 years, > 9 years). Blocks of fixed size will be used within each of the randomization strata.

A separate randomization stratum will be included for the first 12 patients randomized in Japan (the Japanese PK cohort). As 4 patients are needed in each treatment arm in this cohort, these patients will be randomized in a 1:1:2:2 ratio to placebo 3 mg/kg, placebo 4.5 mg/kg, WVE-210201 3 mg/kg, and WVE-210201 4.5 mg/kg. This stratum will not include the age randomization factor. Japanese patients randomized after the Japanese PK cohort will be randomized as described above, but in strata that are separate from the non-Japanese patients.

6.1.2 *Open-label Treatment Period*

Patients randomized to WVE-210201 will continue with the dose level administered at the end of the Double-blind Treatment Period. Patients randomized to placebo will be treated with WVE-210201 at the dose level they had received at the end of the Double-blind Treatment Period. Patients and clinical site staff will remain blinded to the patient's treatment assignment from the Double-blind Treatment Period.

6.2 Dose and Study Drug Administration of Investigational Drug or Placebo

6.2.1 *Identity of Investigational Drug*

6.2.1.1 *WVE-210201*

WVE-210201 will be supplied as an isotonic solution for dilution for IV infusion. Directions on dilution are provided in the Pharmacy manual.

Laboratory Code: WVE-210201

Chemistry: WVE-210201 drug substance may be described chemically as the fully neutralized sodium salt of a 3'→5' linked mixed 2'-fluoro - 2'-deoxy-*2'-O*-methyl- ribonucleic acid oligonucleotide 20 mer containing a prescribed combination of phosphodiester and phosphorothioate linkages.

International Nonproprietary Name (INN): Not yet assigned

United States Adopted Name (USAN): suvodirsen

Molecular Formula (sodium salt form): C₁₉₆H₂₁₁F₁₅N₇₆Na₁₉O₁₀₈P₁₉S₁₅

Average Molecular Weight (sodium salt form): 7150.45 g/mol

Molecular Formula (free acid): C₁₉₆H₂₃₀F₁₅N₇₆O₁₀₈P₁₉S₁₅

Average Molecular Weight (free acid): 6732.80 g/mol

6.2.1.2 *Placebo*

To maintain the blind, a matched placebo will be supplied as the comparator treatment. Matched placebo consisting of a liquid phosphate buffered saline solution will be supplied in single-use glass vials for dilution for IV infusion. The placebo will be visually identical in appearance to WVE-210201 drug product.

6.2.2 *Administration of Study Drug*

The study drug, WVE-210201 or placebo, are supplied as a solution in a single-use vial. Study drug should be diluted with 0.45% Sodium Chloride Injection or 0.9% Sodium Chloride Injection prior to infusion, in accordance with instructions in the Pharmacy Manual. Study drug will be administered at the study site by trained personnel. The route of administration will be IV, and the total volume of the infusion will be 100-500 mL based on patient weight.

The infusion should be administered over a minimum of 60 minutes. However, investigators should consider initiating treatment with longer infusion times (i.e., 3 hours) to potentially enhance tolerability. The prepared infusion solution contains no preservatives and should be administered within 4 hours of preparation. Patients should remain stationary during the infusion. For each dosing day, ± 2 days of window may be allowed. However, administration of Study Drug needs to be separated by a minimum of 5 days between infusions. The Investigator may electively choose to monitor patients in an in-patient setting on any dosing day in order to facilitate careful observation of the patient post-study drug administration. However, any such hospitalizations for observation purposes must be pre-planned before the applicable study drug administration day and clearly documented in the patient's medical record. Please see [Section 9](#) for additional information regarding hospitalization.

6.2.3 *Monitoring for Infusion-Associated Reactions*

As with other IV-infused drugs, infusion-related reactions (e.g., rash, urticaria, erythema, pruritus, bronchospasm, pyrexia, and hypotension) may occur with WVE-210201. Infusion-associated reactions such as pyrexia, vomiting, tachycardia, and chills have been observed in clinical studies of WVE-210201 or placebo. Symptoms such as flushing, pyrexia, skin reactions, dyspnea, lower back pain, hypotension, nausea and/or vomiting, or tachycardia may require

temporary interruption of the infusion or slowing the infusion rate for the subsequent dosing. Patients who experience infusion-associated reactions may be pre-medicated for subsequent infusions to help ameliorate symptoms, as medically appropriate, per local guidelines and clinical practice. However, severe or serious reactions, such as hypotension requiring treatment, dyspnoea requiring bronchodilators, angioedema or generalized urticaria require immediate discontinuation of the study drug administration, aggressive symptomatic therapy, and the patient should not be re-challenged.

